6.4 Storage and Accountability

All study drugs must be kept in a secure location under appropriate storage conditions (see investigator brochure). The medication provided for this study is for use only as directed in the protocol. GWU Medical Faculty Associates will be responsible for the storage, handling, and dispensing of study drug. GWU Medical Faculty Associates will monitor all documentation related to drug handling activities to ensure adherence to proper procedures. At each study visit, GWU Medical Faculty Associates will dispense the required study medication needed until the next study visit.

All used and unused study drugs must be retained at the clinic for reconciliation and accountability and should be destroyed at the study site by authorized personnel according to approved procedures or collected by the monitor for disposal.

7.0 TREATMENT PLAN

All subjects must sign the informed consent form (ICF) and if applicable privacy authorization for release of health information prior to initiating any screening procedures including: discontinuing/changing or withholding (washout) of any medication. It is expected that after being consented, if any subject is using a

concomitant medication where his/her dosage has not met the stable dose time frame outlined in Section 5.0 the subject will be asked to return to the site after the appropriate timeframe to complete the Visit 1 procedures. This return to the site would be considered a continuation of screening visit. At no time should a subject withhold medication prior to signing the ICF. The visit schedule is outlined in "Treatment Protocol Schedule."

The original signed patient consent form will be kept in the patient's source document study folder and maintained at the clinical site. A copy of the signed patient consent form will be given to the study participant.

7.1. Details on Treatment Schedule and Procedures

A schedule of all study visits and assessments is provided in Appendix E, table 1. Appendix E, Table 2 provides all laboratory studies being performed on screening and throughout the trial. **Patient should be encouraged to adhere to the study visit schedule unless an emergency occurs preventing compliance.**

Screening/enrollment

Subjects will be screened at the screening visit to determine their eligibility for enrollment. The following data are to be collected at Screening Visit for every patient and recorded in the CRF.

- Obtain written informed consent for screening and treatment phase of study, and privacy authorization for release of medical information to include muscle biopsy results and tissue if done previously.
- Demographics: date of birth, sex, race
- Diagnosis of definite or probable JDM by Bohan and Peter criteria (or JDM by newly-developed myositis classification criteria after approval by American College of Rheumatology), and date of diagnosis
- Review inclusion and exclusion criteria for eligibility for study and verify that inclusion/exclusion criteria have been met
- Obtain and record medication history
- Obtain referring physician's contact information, patient release to share information, and agreement with patient's potential entry into trial
- Medical and surgical history: past and current medical and surgical history relevant for purpose of the study.
- Vital signs: height (m), weight (kg), pulse (beats/min), blood pressure (mmHg), and pulse oximetry
- History and physical examination
- Core set measures: CMAS, MMT-8, MDAAT (Extra-muscular Global activity), MD global activity (VAS), MD global damage (VAS), Patient-parent global activity (VAS), CHAQ/HAQ

- Obtain laboratory samples for clinical chemistry (Chem-20, GGT), complete blood count (CBC) with differential, urinalysis, muscle enzymes (CK, LDH, aldolase, AST, ALT), GGT; serologies: HIV antibody, Hepatitis B surface antigen, Hepatitis B core antigen, and hepatitis C antibody, CD19 (for those who received rituximab before) Quantiferon will be completed at the screening visit. If the Quantiferon is indeterminate, then a T spot or PPD will be done.
- Urinalysis
- Collect urine sample for pregnancy for females of child bearing potential (where applicable) Post-menopausal females defined as \geq age 60 and twelve (12) consecutive months of amenorrhea (lack of menstruation) will not be required to undergo pregnancy testing
- Perform radiographic examination of chest

Some patients may wish to obtain screening labs at home and present the results at the screening visit. This would enable them to enter the intervention phase at the same visit as the screening visit. Results dated within 6 weeks prior to screening visit will be accepted to satisfy eligibility criteria.

All safety labs during the regular study visit may be completed at the home institution up to 10 days prior to the visit and reports sent to GW.

A re-screen protocol will be followed if a period of greater than 45 days elapses between the screening visit and start of treatment.

Visit 1/Week 0 (Intervention phase)

Visit 1(week 0) will occur 0- 45 days after all initial screening evaluations are concluded and the results of screening testing procedures are completed. The subject must remain in the clinic for 15 minutes following administration of study drug. The following evaluations/procedures will be performed at this visit.

- Review of inclusion/exclusion criteria
- NCI Common Toxicity Assessment
- Obtain vital signs (HR,BP,RR, oral temperature and weight, and if indicated, by history of shortness of breath or lung disease, pulse oximetry)
- Medical history and perform a full physical examination
- Collect urine sample for pregnancy test for females of child bearing potential prior to administration of study medication (where applicable)
- Core set activity measures: physician global activity, patient/parent global activity, manual muscle testing (MMT-8), CMAS, HAQ/CHAQ, MDAAT, muscle enzymes, CHQ PF-50/SF- 36, and Disease Activity Score (DAS)
- Myositis Damage Index (MDI): assessment of disease damage completed by the physician during physical examination.
- Physician global damage (VAS)
- Dermatology assessment: CDASI, MD Global Skin Activity + Damage (Optional)
- CDASI, photographs of skin rashes, periungual nailfold capillary assessment.

- Quality of life questionnaires: CHQ PF-50/SF- 36, Dermatology Life Quality Index (DLQI), PROMIS/fatigue, Peds QL fatigue
- Muscle MRI: bilateral thighs and pelvis, axial STIR and T1 images
- Plain radiographs for calcinosis for patients with calcinosis
- Obtain blood samples for Chem-20, GGT, CK, aldolase, LDH, CBC with diff., TSH, anti-thyroid antibodies, von Willebrand Factor antigen level, quantitative immunoglobulins (IgG, IgM, IgA), ANA, ENA, dsDNA, Lymphocyte flow cytometry (TBNK cells)
- Urinalysis
- Collect pre -treatment research blood samples for Immunophenotyping (T, B cells and macrophages), gene expression, and cytokine/chemokine analysis (see Section 3.1.h)
- Myositis specific and associated autoantibody testing
- Collect pre -treatment blood samples for immunogenicity
- Pregnancy test for females of child bearing potential (where applicable)
- Administer first dose of study medication and observe after the injection for at least 15 minutes
- Schedule and instruct the subject to return for the next visit, teaching injection technique, review medication administration log.

Phone follow-up #1 (14 days (+/- 7 days after visit 1)

- Adverse events will be reviewed and recorded (NCI Common Toxicity criteria version 4.0).

Phone follow-up #2 (will occur 28 days (+/- 7 days) after visit 1.

- Adverse events will be reviewed and recorded.

Visit 2 (week 6) will occur 42 days (+/-10 days) after visit 1

- Review concomitant medication and query for adverse events and document in CRF
- NCI Common Toxicity Assessment
- Obtain vital signs (HR, BP, RR, oral temperature and weight) and if indicated, by history of shortness of breath or lung disease, pulse oximetry)
- Medical history and perform a full physical examination
- Collect urine sample for pregnancy test for females of child bearing potential prior to administration of study medication (where applicable)
- Core set activity measures: physician global activity, patient/parent global activity, manual muscle testing (MMT-8), CMAS, HAQ/CHAQ, MDAAT, muscle enzymes, CHQ PF-50/SF- 36, and Disease activity score (DAS), physician global damage (VAS)
- Dermatology assessment: CDASI, photographs of skin rashes
- Quality of life questionnaires: CHQ PF-50/SF- 36, DLQI, PROMIS/fatigue, and Peds QL fatigue
- Physician and patient/parent assessment of study outcome

- Obtain blood samples for Chem-20, GGT, CK, aldolase, LDH, CBC with diff., von Willebrand Factor antigen level [**may be performed at home institution, up to 10 days before the visit date**]
- Urinalysis
- Collect urine sample for pregnancy test for females of child bearing potential (where applicable)
- Prednisone taper may commence using a predetermined schedule (section 5) if the patient has achieved the Definition of Improvement (DOI) and is rated by the study physician as at least minimally improved.
- Review log of medication self-administration and pharmacy to dispense study medication needed before next visit
- Administer dose of study medication and observe after the injection for at least 15 minutes
- Schedule and instruct the subject to return for the next visit

Phone follow-up #3 (14 days (+/- 7 days after visit 2))

- Adverse events will be reviewed and recorded (NCI Common Toxicity criteria version 4.0).

Phone follow-up #4 (will occur 28 days (+/- 7 days) after visit 2.)

- Adverse event will be reviewed and recorded.

Visit 3 (week 12) will occur 42 days (+/- 10) days after Visit 2

- Review concomitant medication and query for adverse events and document in CRF.
- NCI Common Toxicity Assessment
- Obtain vital signs (HR,BP,RR, oral temperature and weight) and if indicated , by history of shortness of breath or lung disease, pulse oximetry)
- Medical history and perform a full physical examination
- Collect urine sample for pregnancy test for females of child bearing potential prior to administration of study medication (where applicable)
- Core set activity measures: physician global activity, patient/parent global activity, manual muscle testing (MMT-8), CMAS, HAQ/CHAQ, MDAAT, muscle enzymes, CHQ PF-50/SF- 36, and Disease activity score (DAS), physician global damage (VAS)
- Quality of life questionnaires: CHQ PF-50/SF- 36,DLQI , PROMIS/fatigue and Peds QL fatigue
- Physician and patient/parent assessment of study outcome
- Dermatology assessment performed by Rheumatologist : CDASI, photographs of skin rashes, periungual nailfold capillary assessment Dermatology Assessment Performed by Derm: CDASI, MD Global Skin Activity + Damage (Optional)

- Obtain blood samples for Chem-20, GGT, CK, aldolase, LDH, CBC with diff., von Willebrand Factor antigen level, Lymphocyte flow cytometry (TBNK cells) [**may be performed at home institution, up to 10 days before the visit date**]
- Urinalysis
- Collect research blood samples for Immunophenotyping (T, B cells and macrophages), gene expression and cytokine/chemokine analysis (see Section 3.1.h)
- Review if patient improved by $\geq 5\%$ in at least 3 of 6 core set measures (by IMACS or PRINTO measures). If patient did not meet this criterion and was rated by the study physician as unchanged or worsened since visit 1, an option to increase the dose to 212 mg (87.5 + 125 mg) SQ weekly for subjects with body weight ≥ 50 kg or to increase the dose to 137.5 mg (87.5 mg + 50 mg) for subjects with body weight < 50 kg will be presented.
- Prednisone taper may commence using a predetermined schedule (section 5) If the patient has achieved the Definition of Improvement (DOI) and is rated by the study physician as at least minimally improved.
-
- Collect blood samples prior to the injection at Week 12 for PK and immunogenicity assessment
-
- Review log of medication self-administration and pharmacy to dispense study medication needed before next visit
- Administer dose of study medication and observe after the injection for at least 15 minutes
- Schedule and instruct the subject to return for the next visit

Phone follow-up #5 (14 days (+/- 7 days after visit 3))

- Adverse events will be reviewed and recorded (NCI Common Toxicity criteria version 4.0).

Phone follow-up #6 (will occur 28 days (+/- 7 days) after visit 3.)

- Adverse event will be reviewed and recorded.

Visit 4 (week 18) will occur 42 days (+/-10 days) after visit 3

- Review concomitant medication and query for adverse events and document in CRF.
- NCI Common Toxicity Assessment
- Obtain vital signs (HR, BP, RR, oral temperature and weight) and if indicated, by history of shortness of breath or lung disease, pulse oximetry)

- Medical history and perform a full physical examination
- Collect urine sample for pregnancy test for females of child bearing potential prior to administration of study medication (where applicable)
- Core set activity measures: physician global activity, patient/parent global activity, manual muscle testing (MMT-8), CMAS, HAQ/CHAQ,MDAAT, muscle enzymes, CHQ PF-50/SF- 36, and Disease activity score (DAS), physician global damage (VAS)
- Quality of life questionnaires: CHQ PF-50/SF- 36,DLQI, PROMIS/fatigue and Peds QL fatigue
- Physician and patient/parent assessment of study outcome
- Obtain blood samples for Chem-20, GGT, CK, aldolase, LDH, CBC with diff., von Willebrand Factor antigen level [**may be performed at home institution, up to 10 days before the visit date**]
- Urinalysis
- Prednisone taper may commence using a predetermined schedule (section 5) If the patient has achieved the Definition of Improvement (DOI) and is rated by the study physician as at least minimally improved.
- Review log of medication self-administration and pharmacy to dispense study medication needed before next visit
- Administer dose of study medication and observe after the injection for at least 15 minutes
- Schedule and instruct the subject to return for the next visit

Phone follow-up #7 (14 days (+/- 7 days after visit 4)

- Adverse events will be reviewed and recorded (NCI Common Toxicity criteria version 4.0).

Phone follow-up #8 (will occur 28 days (+/- 7 days) after visit 4.

- Adverse event will be reviewed and recorded.

Visit 5 (week 24) will occur 42 days (+/- 10) days after Visit 4 (End of Study Treatment or Early Termination)

- Review concomitant medication and query for adverse events and document in CRF.

- NCI Common Toxicity Assessment
- Obtain vital signs (HR,BP,RR, oral temperature and weight) and if indicated , by history of shortness of breath or lung disease, pulse oximetry)
- Medical history and perform a full physical examination
- Collect urine sample for pregnancy test for females of child bearing potential prior to administration of study medication (where applicable)
- Core set activity measures: physician global activity, patient/parent global activity, manual muscle testing (MMT-8), CMAS, HAQ/CHAQ, MDAAT, muscle enzymes, CHQ PF-50/SF- 36, and Disease activity score (DAS)
- Quality of life questionnaires: CHQ PF-50/SF- 36, DLQI , PROMIS/fatigue and Peds QL fatigue
- Myositis Damage Index (MDI): assessment of disease damage completed by the physician during physical examination. Physician global damage (VAS)
- Physician and patient/parent assessment of study outcome
- Dermatology assessment performed by Rheumatologist: CDASI, photographs of skin rashes, periungual nailfold capillary assessment
- Dermatology Assessment performed by Dermatologist: CDASI, MD Global Skin Activity + Damange (Optional)
- Prednisone taper may commence using a predetermined schedule (section 5) If the patient has achieved the Definition of Improvement (DOI) and is rated by the study physician as at least minimally improved..
- Muscle MRI: bilateral thighs and pelvis, axial STIR and T1 images
- Plain radiographs for calcinosis for patients with calcinosis
- Obtain blood samples for Chem-20,GGT, CK, aldolase, LDH, CBC with diff., TSH, anti-thyroid antibodies, von Willebrand Factor antigen level, quantitative immunoglobulins (IgG, IgM, IgA), ANA, ENA, dsDNA, Lymphocyte flow cytometry (TBNK cells) [**may be performed at home institution, up to 10 days before the visit date**]
- Collect research blood samples for Immunophenotyping (T, B cells and macrophages), gene expression and cytokine/chemokine analysis (see Section 3.1.h)
- Urinalysis
- Review log of medication self-administration
- Collect blood samples prior to the injection at Week 24 for PK and immunogenicity assessment
- Prednisone taper may commence using a predetermined schedule (section 5) if the patient has achieved the Definition of Improvement (DOI) and is rated by the study physician as at least minimally improved.
- Administer dose of study medication (abatacept) and observe after the injection for at least 15 minutes
- Patient terminates study enrollment and all study supplies are returned, or patient will continue on open-label extension: schedule and instruct the subject to return for the next visit

- An open label extension phase will be offered for up to 6 months for patients meeting the definition of improvement and who are rated by their study physician as at least minimally improved.
- If the subject chooses not to continue to be in the open label extension phase of the trial, the subject will be referred back to his/her local rheumatologist for further care. Subject terminates study enrollment and all study supplies are returned
- Subjects will receive their last injection of abatacept at week 24 even if they do not want to continue in the open label extension phase of the trial

Open label extension Visit (will occur within 6 months of visit 5)

An open label extension phase of up to 6 months duration will be offered to all patients meeting the definition of improvement and who are also rated as at least minimally improved from the baseline visit (visit 1). Patients must commit to at least one follow-up visit within 6 months of visit 5, which will be at their own expense for travel and testing costs. At each follow-up visit, the following will be performed:

- Review concomitant medication and query for adverse events and document in CRF.
- NCI Common Toxicity Assessment
- Obtain vital signs (HR,BP,RR, oral temperature and weight) and if indicated , by history of shortness of breath or lung disease, pulse oximetry)
- Medical history and perform a full physical examination
- Collect urine sample for pregnancy test for females of child bearing potential prior to administration of study medication (where applicable)
- Core set activity measures: physician global activity, patient/parent global activity, manual muscle testing (MMT-8), CMAS, HAQ/CHAQ,MDAAT, muscle enzymes, CHQ PF-50/SF- 36, and Disease activity score (DAS), physician global damage (VAS)
- Physician and patient/parent assessment of study outcome
- Obtain blood samples for Chem-20, GGT, CK, aldolase, LDH, CBC with diff.,
- Urinalysis
- Review log of medication self-administration
- Prednisone taper may commence using a predetermined schedule (section 5) If the patient has achieved the Definition of Improvement (DOI) and is rated by the study physician as at least minimally improved.
- Administer dose of study medication and observe after the injection for at least 15 minutes
- Patient terminates open-label extension. Patient is referred back to referring rheumatologist.

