3.1 ENDPOINTS

Primary

The *primary endpoint* of this trial is to establish safety and efficacy of Abatacept in patients with refractory Juvenile Dermatomyositis

- a) Safety: Abatacept will be well-tolerated and safe.
- b) Improvement in myositis disease activity: the published IMACS myositis definition of improvement will be achieved in at least 6 of 10 patients at the end of the trial (38).

Secondary

- a) To evaluate the response rate to Abatacept in JDM using the PRINTO definition of improvement, including criteria for minimal, moderate and major clinical response (40, 41).
- b) To evaluate the response rate to Abatacept using newly developed criteria for myositis clinical response, which are pending ACR-EULAR approval (Appendix D2), as well as other top performing criteria considered at the International Myositis Response Criteria Consensus Conference.
- c) To examine response to treatment in individual core set measures of disease activity as developed by IMACS, including physician and patient/parent global activity, muscle strength (by manual muscle testing), physical function (by HAQ/CHAQ), muscle enzymes, and extra-muscular activity (by the Myositis Disease Activity Assessment Tool)

- d) To examine other core set activity measures as developed by PRINTO, including the Childhood Myositis Assessment Scale, the Disease Activity Score and CHQ-PF50
- e) Steroid-sparing benefit: 20% reduction of the corticosteroid therapy will be achieved in 6 of 10 patients at the end of the trial
- f) To examine improvement in patient reported outcomes, including health-related quality of life and fatigue measures, including the PROMIS and PedsQL fatigue questionnaires. Both patient and parent questionnaires will be obtained, for patients < 18 years of age.
- g) To examine improvement in cutaneous activity, using the Cutaneous Dermatomyositis Area and Severity Index (CDASI) and the Dermatology Life Quality Index, as well as periungual nail fold capillary density. To document changes in cutaneous findings by standardized photography.
- h) To examine improvement in muscle inflammation by examining a thigh/pelvis STIR MRI at baseline and 6 month follow-up. MRI readings will be blinded to the clinical assessment information, including, if possible, date of assessment, and study drug dose.
- i) To examine that disease damage does not increase while under treatment with abatacept, by examining the Myositis Damage Index at baseline and 6 month follow-up.

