9.0 DISCONTINUATION OF SUBJECTS

Subjects in this study may be discontinued for any of the following reasons:

- Severe allergic reaction to the study medication
- Participation in another investigational drug study
- Any medical condition which, in the opinion of the investigator, warrants discontinuation from the study for the safety of the patient, either as a cause of the study drug or Protocol violations, including non-compliance or inability to perform protocol-required procedures
- Voluntary withdrawal (withdrawal of consent)
- Pregnancy
- Instruct WOCBP to contact the investigator or study staff immediately if they suspect they might be pregnant (e.g., missed or late menstrual period) at any time during study participation. Institutional policy and local regulations should determine the frequency of on-study pregnancy tests for WOCBP enrolled in the study.
- The investigator will notify BMS if a study subject becomes pregnant.
- Loss of ability to freely provide consent through imprisonment or involuntary incarceration for treatment of either a psychiatric or physical (e.g., infectious disease) illness.
- If 3 or more patients develop a serious adverse event thought to be related to study drug, no new patients will be enrolled into the study until the adverse events have been reviewed by the Medical Safety Officer and/or Data Safety Monitoring Board.

Criteria for Disease Worsening (Appendix F):

Criteria for disease worsening in a clinical trial, by which patients could be termed treatment failures and offered alternative therapies, were preliminarily defined by IMACS. They will be incorporated into this trial and include:

- Physician global worsening of ≥ 2 cm on the 10 cm visual analog scale (VAS) and a worsening of the manual muscle testing by $\geq 20\%$, or
- Global extra muscular organ disease activity (a composite of constitutional, cutaneous, skeletal, gastrointestinal, pulmonary and cardiac activity) worsening by ≥ 2 cm on a 10 cm VAS, or
- 3 of any 6 IMACS core set activity measures worse by $\geq 30\%$.

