15.0 STATISTICS/DATA ANALYSIS

Statistical Plan:

This is an open label nonrandomized trial to assess the safety and efficacy of subcutaneous abatacept in 10 patients (children and adults) with juvenile onset refractory dermatomyositis (JDM).

We postulate that at least 6 of 10 patients with JDM will meet the myositis preliminary definition of improvement (DOI) after receiving 24 weeks of therapy with abatacept. Data will be entered and stored in the RedCap database, licensed to George Washington University. Primary analyses will be performed using intention to treat regardless of compliance with therapy or trial protocol. We will also perform analyses that include only those participants with known outcome data.

Summary statistics will be generated to describe the study samples. Descriptive statistics, including measures of central tendency (e.g. means, medians) and estimates of spread (e.g. standard deviations) will be used for continuous variables, including reporting of adverse event frequencies, core set measure assessments, and demographic and clinical variables. Non-parametric Wilcoxon signed rank tests will be used to investigate changes in continuous variables. 95% confidence intervals will be calculated for all point estimates.

We will examine the percentage of subjects meeting the DOI (20%), as well as moderate (DOI 50%) or major improvement criteria (DOI 70%), as well as frequency of patients achieving clinically inactive disease.

Due to the small number of subjects, it is unlikely that any statistical test would have the power to detect significant differences in any of the measured variables. We will therefore look not only at the percentage of subjects meeting improvement criteria by the DOIs, but also look for an improvement in individual core set myositis disease activity measurements of muscular and extra-muscular disease activity, as well as the in the patient-reported outcome measures, cutaneous assessments and MRI. We will also examine responsiveness after treatment using standardized response means and correlation degree of change between the measures. Differences between initial

and 24 weeks values will be analyzed by Student t distribution and Wilcoxon matched pair tests.

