APPENDIX E TABLE 1 AND TABLE 2 /2a: STUDY SCHEDULE OF EVENTS

Table 1.

Study Events	Treatment Week														
	Screening	W0	W2	W4	W6	W8	W10	W12	W14	W16	W18	W20	W22	W24	W25-W48
Visit	V1				V2			V3			V4			V5	V6 (extension)
Phone f/up*			X	X		X	X		X	X		X	X		
Informed Consent/Assent	X														
Inclusion/Exclusion Criteria	X														
Vital signs, Weight, (pulse oximetry) is changed to screening evaluation	X	X			X			X			X			X	X
Brief physical evaluation		X			X			X			X			X	X
CMAS	X	X			X			X			X			X	X
MMT8	X	X			X			X			X			X	X
MDAAT (EM Global only at Screening)	X	X			X			X			X			X	X
Disease Activity Score		X			X			X			X			X	X
MD Global Activity (VAS)	X	X			X			X			X			X	X
Patient/Parent Global Activity (VAS)	X	X			X			X			X			X	X
CHAQ/HAQ	X	X			X			X			X			X	X
CHQ-PF50/SF36		X			X			X			X			X	
Myositis Damage Index		X												X	
Urine Pregnancy , UA,	X	X			X			X			X			X	X
Screening Blood Tests	X														
Research Blood Tests form is changed to blood sample tracking form (regular and research blood test)		X						X						X	
Chest X-ray	X														
Plain radiograph for calcinosis (calcinosis pts only)		X												X	
Muscle MRI (bilateral, Axial and T1)		X												X	
MD Global Disease Damage (VAS)		X			X			X			X			X	X
Physician Assessment of Study Outcome					X			X			X			X	X

Dermatology assessment ([name] Global Skin Activity/Damage performed by Dermatologist) Optional		X						X						X	
CDASI (performed by Rheumatologist)		X			X			X			X			X	X
DLQI, skin itch, Patient and MD skin global activity/damage (performed by Rheumatologist)		X			X			X			X			X	X
Photograph Documentation (if applicable)		X			X			X			X			X	X
Nailfold capillaries photograph (Optional)		X						X						X	X
PROMIS and PedsQL fatigue		X			X			X			X			X	X
Review medication log and self-administration log		X			X			X			X			X	X
NCI CTC Assessment		X			X			X			X			X	X
Adverse Events assessments		X	X	X	X	X	X	X	X	X	X	X	X	X	X
Prednisone taper if meet DOI and rated at least minimally improved					X			X			X			X	X
Increase Abatacept dose if ≤ 5% improved by DOI and rated as unchanged or worsened								X							
Administer Abatacept medication		X			X			X			X			X	X
Visit		V1			V2			V3			V4			V5	V6
Week	Screening	W0	W2	W4	W6	W8	W10	W12	W14	W16	W18	W20	W22	W24	W25-W48

*Phone f/up at W2, 4, 8, 10, 14, 16, 20, and 22 will consist of evaluation of Adverse Events.

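### Early termination shares the Visit 5 (week 24) list: its injection item is not reconciled with the reasons for discontinuation, and the plan does not say how an early-termination DOI enters the primary count

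*Combined protocol and SAP*

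**What the plan says.** **Visit structure.** Section 7.1 heads the last treatment-phase visit "Visit 5 (week 24) will occur 42 days (+/- 10) days after Visit 4 (End of Study Treatment or Early Termination" and gives a single list of procedures under it. The list includes the core set measures that make up the DOI and, with no condition, "Administer dose of study medication (abatacept) and observe after the injection for at least 15 minutes". In Appendix E Table 1 the row "Administer Abatacept medication" is marked at W24/V5, and the table has no column for early termination.

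**Leaving the trial.** Section 9.0 opens with "Subjects in this study may be discontinued for any of the following reasons" and lists, among others, "Severe allergic reaction to the study medication" and pregnancy. Later it recommends a termination evaluation for anyone who leaves after receiving drug, without giving its content. It also encourages everyone who has had at least one dose to stay and complete all visits.

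**Endpoint.** Section 3.1, primary (b), reads "the published IMACS myositis definition of improvement will be achieved in at least 6 of 10 patients at the end of the trial". The synopsis also uses the end of the trial. Section 15.0 postulates that at least 6 of 10 patients "will meet the myositis preliminary definition of improvement (DOI) after receiving 24 weeks of therapy with abatacept", and Section 2.1 likewise refers to 24 weeks of therapy. Section 15.0 makes the primary analysis intention to treat, whatever the compliance, and adds an analysis limited to participants whose outcome is known. It has no rule for missing or early readings.

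**The concern.** The shared heading creates two separate problems.

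The first is procedural. Section 9.0 recommends a termination evaluation but does not describe it, so the Visit 5 list is the only written content for it. Followed literally, that list puts an abatacept injection in front of a patient who is leaving for a reason named in Section 9.0.

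The second concerns the primary result. Core set measures taken at early termination fall under the Visit 5 heading. If the end of the trial is read as the end of that patient's participation, a DOI met at, say, week 8 could be counted as a success, although Sections 2.1 and 15.0 describe a result after 24 weeks of therapy. The same reading could be treated as a known outcome in the additional analysis. In an open-label, single-arm trial with a fixed target of 6 of 10, that rule should not be left until the data have been seen.

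**Working it through.** **Step 1. Dosing text, side by side.**

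- Section 7.1, Visit 5: the heading covers both end of treatment and early termination, and the injection item carries no condition.
- Section 7.1, same list: a pregnancy test precedes dosing, but this step states no consequence of a positive result.
- Section 7.1, last-injection sentence: "Subjects will receive their last injection of abatacept at week 24 even if they do not want to continue in the open label extension". It concerns week 24 and patients who decline the extension, and is silent on early termination.
- Section 9.0: severe allergic reaction and pregnancy are reasons for discontinuation, and the termination evaluation is not described.
- Appendix E Table 1: injection marked at W24/V5, no separate column.

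None of these places exempts an early leaver from the injection item, so the list and Section 9.0 are unreconciled on paper.

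**Step 2. Endpoint text, side by side.** Sections 2.1 and 15.0 give a time after 24 weeks of therapy; the synopsis and Section 3.1(b) give the end of the trial. Nothing says that an early-termination DOI is the week-24 outcome, and nothing says that it is not. Because leavers are encouraged to keep attending, one patient could have both an early-termination DOI and a week-24 DOI, with no rule for which governs.

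**Step 3. The plan's own figure.** The target of 6 of 10 is a postulate. The plan gives no null rate, power or derivation, so there is nothing to reproduce.

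**Step 4. Effect of one patient.** One of 10 is 1/10 = 10 percentage points. Assumed case: 5 responders and 4 non-responders at week 24, plus 1 early leaver who met the DOI on leaving. The intervals are exact (Clopper-Pearson): lower limit = 0.025 quantile of Beta(x, n−x+1), upper limit = 0.975 quantile of Beta(x+1, n−x).

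| Handling of the early leaver | Result | 95% CI | Target of 6 |
|---|---|---|---|
| Early DOI counted | 6/10 = 60% | 26.2% to 87.8% | met |
| Counted as not meeting DOI | 5/10 = 50% | 18.7% to 81.3% | missed |
| Left out (known outcome only) | 5/9 = 55.6% | 21.2% to 86.3% | not defined for 9 |

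**Step 5. Chance of reaching the target.** The documents give no DOI rate or dropout rate, so both are assumed, as is an equal DOI probability p for an early and a week-24 reading. With k early leavers counted as not meeting the DOI, m = 10 − k patients can still respond, and P(X ≥ 6) = Σ C(m,x) pˣ(1−p)^(m−x) for x = 6 to m. If early readings count, m = 10.

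| Assumed p | Early readings count | k = 1 | k = 2 | k = 3 |
|---|---|---|---|---|
| 0.5 | 0.377 | 0.254 | 0.145 | 0.062 |
| 0.6 | 0.633 | 0.483 | 0.315 | 0.159 |
| 0.7 | 0.850 | 0.730 | 0.552 | 0.329 |
| 0.8 | 0.967 | 0.914 | 0.797 | 0.577 |

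**Step 6. What the visit label can tell.** Each visit is timed from the one before, so Visit 5 within all windows falls at 4 × 42 ± 4 × 10 = 168 ± 40 days, that is day 128 to 208 (weeks 18.3 to 29.7). An early-termination reading can fall at any point after the first dose. The label alone therefore does not identify a week-24 assessment; the study day is needed.

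**The case against.** **On the outcome.** A reader might infer that the plan files an early DOI as the week-24 primary outcome. The documents do not support that. Sections 2.1 and 15.0 require 24 weeks of therapy, which a week-8 leaver has not had. The end of the trial in Section 3.1 most naturally means the same time point. Intention to treat says who is analysed, not which reading stands for week 24. The case report form is not in the documents, so how an early reading would be labelled or dated is unknown. What stands is that no rule is written.

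**On dosing.** A reader might also infer that the protocol orders an injection for a patient withdrawn for allergy or pregnancy. That too goes beyond the text. Discontinuation is worded permissively, continuation after a serious adverse event goes to discussion with the Medical Safety Officer and/or the Data Safety Monitoring Board, and a clinician would probably not follow the list literally. Other items on the list do not add to the conflict: the PK sample is tied to the week-24 injection, and the prednisone taper and the extension offer both require the DOI plus at least minimal improvement. None of this attaches a condition to the injection item.

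**On size.** The change from 5 to 6 needs an early leaver who met the DOI on leaving and exactly five other responders. Some who stop drug will still attend week 24, as Section 9.0 encourages. The plan is descriptive and disclaims power. These points limit how often the gap would matter; they do not close it.

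**Conclusion.** The concern holds in two limited parts. First, the shared Visit 5 list contains an unconditional injection item that is not reconciled with Section 9.0, and Appendix E offers no separate column. This is a contradiction between written procedures, not evidence that any patient would be dosed wrongly. Second, the plan neither directs nor prevents counting an early-termination DOI toward the 6 of 10. One such patient is worth 10 percentage points and can decide whether the target is met. At an assumed true DOI rate of 0.6, the chance of reaching 6 of 10 is 0.633 if early readings count, 0.483 if one early leaver counts as not meeting the DOI, and 0.315 if two do. The DOI rates, the numbers of early leavers and the equal response probability are illustrations; the textual gap does not depend on them.

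**What to change.** 1. In Section 7.1 and Appendix E Table 1, separate early termination from Visit 5. Keep the same assessments and record the study day.
2. Reconcile the injection item in Section 7.1 and Appendix E with the reasons for discontinuation and the termination evaluation in Section 9.0. The clinical rule is for the investigators and the sponsor to set.
3. Align the synopsis and Section 3.1(b) with Section 15.0: only a DOI assessed at the week-24 visit, within a stated window, counts in the primary intention-to-treat count out of 10. This includes patients who stopped drug but attended, so Section 15.0 should say that its reference to 24 weeks of therapy fixes the time of assessment.
4. Count patients with no week-24 assessment as not meeting the DOI. This is one of several defensible conventions; what matters is fixing it in advance. List early-termination DOIs separately or use them in a sensitivity analysis, and say whether they qualify as known outcome data.

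The cost is some protocol wording and one schedule column, with no new procedures. The downside is that the headline responder count may be slightly lower.
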